12 ADVERSE EVENT REPORTING: LIST AND REPORTING REQUIREMENTS

Adverse event (AE) monitoring and reporting is a routine part of every clinical trial. The following list of reported and/or potential AEs and the characteristics of an observed AE will determine whether the event requires expedited reporting **in addition** to routine reporting.

12.1 Expected Toxicities

Adverse Event List(s) for Nivolumab

Categorization of AEs Potentially Associated with Nivolumab

In order to characterize AEs of special clinical interest that are potentially associated with the use of nivolumab, the Sponsor identified select AEs based on the following 4 guiding principles:

- AEs that may differ in type, frequency, or severity from AEs caused by non-immunotherapies
- AEs that may require immunosuppression (e.g., corticosteroids) as part of their management
- AEs whose early recognition and management may mitigate severe toxicity
- AEs for which multiple event terms may be used to describe a single type of AE, thereby necessitating the pooling of terms for full characterization

Based on these guiding principles and taking into account the types of AEs already observed across studies of nivolumab monotherapy, endocrinopathies, diarrhea/colitis, hepatitis, pneumonitis, nephritis, and rash are currently considered to be select AEs. Multiple event terms that may describe each of these are grouped into endocrine, GI, hepatic, pulmonary, renal, and skin select AE categories, respectively. The list of AEs belonging to select AE categories may evolve as more safety information becomes available in the nivolumab program.

Hypersensitivity/infusion reactions were also analyzed along with the select AE categories because multiple AE terms may be used to describe these events, and therefore, pooling of terms provides a more complete characterization of the events. Hypersensitivity/infusion reactions do not, otherwise, meet criteria to be considered select AEs.

Serious Adverse Events Reported from Clinical Trials with Nivolumab Monotherapy

As of June 2017, the following serious AEs have been reported in clinical studies in which nivolumab was given as monotherapy. The frequency of ADRs is defined using the following convention: very common ($\geq 1/10$); common ($\geq 1/100$ to $< 1/10$); uncommon ($\geq 1/1,000$ to $< 1/100$); rare ($\geq 1/10,000$ to $< 1/1,000$); and very rare ($< 1/10,000$). For further information, including SAEs that are rarely associated, please reference the IB.

The following **common** SAE is associated: pneumonitis, diarrhea

The following **uncommon** SAEs by system organ class are associated:

- Endocrine: Adrenal insufficiency, Hypothyroidism
- Gastrointestinal: Abdominal pain, Colitis, Diarrhea, Nausea, Pancreatitis, Vomiting
- General and Administrative Site Conditions: Mucosal inflammation, Pyrexia
- Hepatobiliary: Abnormal hepatic function

- Immune system: Hypersensitivity
- Injury, Poisoning and Procedural Complications: Infusion-related reaction
- Metabolism and Nutrition: Dehydration, Hyperglycemia
- Neurologic: demyelinating polyneuropathy, myasthenic syndrome
- Renal and Urinary: Acute renal failure, Tubulointerstitial nephritis
- Respiratory, Thoracic and Mediastinal Disorders: Dyspnea, Hypoxia, Interstitial lung disease, Lung infiltration, Respiratory failure

Nonserious Adverse Events Reported from Clinical Trials with Nivolumab Monotherapy

As of June 2017, the following nonserious AEs have been reported in clinical studies in which nivolumab was given as monotherapy. The frequency of ADRs is defined using the following convention: very common ($\geq 1/10$); common ($\geq 1/100$ to $< 1/10$); uncommon ($\geq 1/1,000$ to $< 1/100$); rare ($\geq 1/10,000$ to $< 1/1,000$); and very rare ($< 1/10,000$).

The following **very common** nonserious AEs are associated: Fatigue, Diarrhea

The following **common** nonserious AEs are associated: Arthralgia, Asthenia, Cough, Decreased appetite, Pyrexia, Rash, Nausea, Pruritus

A complete list of adverse events observed with nivolumab are detailed in the Investigator's Brochure (IB).

12.2 Expected list of toxicities ONC201:

ONC201 is being evaluated in multiple on-going clinical trials. As of March 15, 2019, 150 patients have been treated with ONC201: 63 patients were male and 87 were female. The age ranged from 2 to 85 years, with 40 (27%) of patients < 18 years old. Seventeen patients received ONC201 on a Q3W schedule, 133 patients received ONC201 on a Q1W schedule. Adults were administered a dose of 625 mg, while children (< 18 years) were dosed from 125 mg to 625 mg depending on body weight.

ONC201 has been well tolerated across the various Phase I clinical trials and administration schedules with dose levels ranging from 125 mg to 625 mg. Only 1 dose reduction (625mg to 500mg) occurred in 1 patient with a Grade 3 neutropenia assessed by the PI as possibly related to ONC201. However, upon re-challenge neutropenia did not recur.

Some patients who received ONC201 have experienced mild or moderate adverse events that were attributed as possibly related to ONC201: fatigue, abdominal pain, fever, nausea, vomiting, anorexia, weakness, elevated serum amylase, neutropenia, bone pain, generalized weakness, allergic reaction, and ataxia.

In summary, ONC201 is well tolerated when administered once every week or once every three weeks at doses ranging from 125 mg to 625 mg.

Side effects seen in animals at exaggerated doses included the following:

- Nausea
- Salivation
- Vomiting
- Abnormal breathing
- Twitching
- Abnormal walking or standing
- Death

A complete list of adverse events observed with ONC201 are detailed in the Investigator's Brochure (IB).

12.3 Adverse Event Characteristics

This study will utilize the descriptions and grading scales found in the NCI Common Terminology Criteria for Adverse Events (CTCAE) version 5.0 for grading all adverse events. All appropriate treatment areas should have access to a copy of the CTCAE version 5.0. A copy of the CTCAE version 5.0 can be downloaded from the CTEP web site (<http://ctep.cancer.gov>).

An Adverse Event (AE) is defined as any untoward medical occurrence in a patient or clinical investigation subject administered a pharmaceutical product and that does not necessarily have to have a causal relationship with this treatment. An AE can therefore be any unfavorable and unintended sign (including an abnormal laboratory finding), symptom, or disease temporally associated with the use of Nivolumab or ONC 201, whether or not considered related to Nivolumab or ONC 201. This includes any newly occurring event or previous condition that has increased in severity or frequency since the administration of drug.

During clinical trials, adverse events can be spontaneously reported or elicited during open-ended questioning, examination, or evaluation of a subject. (In order to prevent reporting bias, subjects should not be questioned regarding the specific occurrence of one or more adverse events.)

Adverse events (AEs) will be recorded in the case report form for the duration of the trial, regardless of whether or not the event(s) are considered related to trial medication.

12.4 Definitions

An adverse event is any new, undesirable medical experience or change of an existing condition that occurs during or after treatment, whether or not considered product-related.

12.4.1 Attribution of the AE:

- Definite – The AE is *clearly related* to the study treatment.
- Probable – The AE is *likely related* to the study treatment.
- Possible – The AE *may be related* to the study treatment.
- Unlikely – The AE is *doubtfully related* to the study treatment.
- Unrelated – The AE is *clearly NOT related* to the study treatment.

Suspected adverse reaction:

BrUOG, for the sponsor-investigator, is required to report in an IND safety report any suspected reaction to the study treatment that is both serious and unexpected.

As per 21 CFR 312.32 (a), the FDA has defined a suspected adverse reaction as any adverse event where there is reasonable possibility that the drug may have caused the adverse event. A reasonable possibility means there is evidence suggesting a causal relationship between the drug and the adverse event.

A suspected adverse reaction outlines the possibility of the causal relationship between the event and the drug, whereas an adverse reaction means the drug caused the event.

12.4.2 Serious Adverse Events (SAE) Definition

An adverse event occurring at any dose that results in any of the following outcomes (CFR 312.32):

- death
- is life-threatening
- inpatient hospitalization or prolongation of existing hospitalization excluding those for study drug administration, transfusion support, disease staging/re-staging procedures, concomitant radiotherapy, thoracentesis / paracentesis, or placement of an indwelling catheter, unless associated with other serious events.
- persistent or significant disability or incapacity,
- congenital anomaly / birth defect.

The definition of serious adverse event (experience) also includes *important medical event*. Medical and scientific judgment should be exercised in deciding whether expedited reporting is appropriate in other situations, such as important medical events that may not be immediately life-threatening or result in death or hospitalization but may jeopardize the patient or may require intervention to prevent one of the other outcomes listed in the definition above. These should also usually be considered serious. Examples of such events are intensive treatment in an emergency room or at home for allergic bronchospasm; blood dyscrasias or convulsions that do not result in hospitalization; or development of drug dependency or drug abuse. A new diagnosis of cancer during the course of treatment should be considered an important medical event.

Unexpected adverse event

An adverse event that is not mentioned in the Investigator's Brochure or package insert or the specificity or severity of which is not consistent with the investigator's brochure or package insert.

Life-threatening

Any adverse drug experience that places the patient or subject, in the view of the investigator, at immediate risk of death from the reaction as it occurred. It does not include a reaction that, had it occurred in a more severe form, might have caused death.

12.4.3 Events requiring reporting as an Important Medical Event:

- **Potential drug induced liver injury** (DILI) is also considered an important medical event.

Potential drug induced liver injury is defined as:

- ALT and/or AST elevation > 3 times upper limit of normal (ULN)
AND
- Total bilirubin > 2 times ULN, without initial findings of cholestasis (elevated serum alkaline phosphatase)
AND
- No other immediately apparent possible causes of AT elevation and hyperbilirubinemia, including, but not limited to, viral hepatitis, pre-existing chronic or acute liver disease, or the administration of other drug(s) known to be hepatotoxic.

Wherever possible, timely confirmation of initial liver related laboratory abnormalities should occur prior to the reporting of a potential DILI event. All occurrences of potential DILIs, meeting the defined criteria, must be reported as SAEs.

- Suspected transmission of an infectious agent (e.g., pathogenic or nonpathogenic) via the study drug is an SAE.
- Although pregnancy, overdose, and cancer (a second primary, excluding non-melanoma skin cancer) are not always serious by regulatory definition, these events must be handled as SAEs.
 - **Pregnancy:** see section for information
 - An **overdose** is defined as the accidental or intentional administration of any dose of a product that is considered both excessive and medically important. All occurrences of overdose must be reported as an SAE.

NOTE: The following hospitalizations are **not considered SAEs**:

- a visit to the emergency room or other hospital department < 24 hours, that does not result in admission (unless considered “important medical event” or event life threatening)
- elective surgery, planned prior to signing consent and which would have been documented to BrUOG at time of registration (otherwise it will be a SAE)
- admissions as per protocol for a planned medical/surgical procedure per study
- routine health assessment requiring admission for baseline/trending of health status (ie, routine colonoscopy)
- medical/surgical admission for purpose other than remedying ill health state and was planned prior to entry into the study. Appropriate documentation is required in these cases and which would have been documented to BrUOG at time of registration
- admission encountered for another life circumstance that carries no bearing on health status and requires no medical/surgical intervention (ie, lack of housing, economic inadequacy, care-giver respite, family circumstances, administrative)

Monitoring of Adverse Events and Period of Observation

Adverse events, both serious and non-serious, and deaths that occur during the patient’s study participation will be recorded in the source documents.

12.5 BRUOG ADVERSE EVENT REPORTING REQUIREMENTS

Investigators are required by Federal Regulation to report adverse drug reactions. Questions regarding drugs as used in this study should be directed to the Brown University Oncology Research Group (BrUOG) Central Office, [contact] [contact], which will in turn notify the Principal Investigator.

All adverse events and special reporting situations, whether serious or non-serious, related or unrelated, will be reported from the time a signed and dated ICF is obtained until 100 days (+1 week) after the last treatment (Nivolumab or ONC201, whichever is last), or until the subject withdraws consent from study participation (declines participation) or at the time patient becomes a screen failure, whichever occurs first. There will be a safety visit at 30 days (+1 week) and 100 days (+1 week) time points.

12.5.1 Pregnancies

Pregnancies occurring while the subject is on study drug or within 100 days (+1 week) after the subject’s last treatment (Nivolumab or ONC201, whichever is last) are considered expedited reportable events. If the subject is on active treatment, the treatment is to be discontinued immediately. The pregnancy must be reported to the Brown University Oncology Research Group, by the site, immediately (within 24 hours of the site being made aware), via the site completed BMS pregnancy reporting Form **and** a 3500A MedWatch form (site to submit to BrUOG), and BrUOG will in turn report to BMS and Oncoceutics immediately (within 1

working day and once in receipt of the site submitted SAE forms). Pregnancies and suspected pregnancies (including a positive pregnancy test regardless of age or disease state) of a female subject occurring while the subject is on treatment (Nivolumab and/or ONC201), or within 100 days (+1 week) of the subject's last treatment (Nivolumab or ONC201, whichever is last), are considered immediately reportable events. Treatment is to be discontinued immediately. The pregnancy, suspected pregnancy, or positive pregnancy test must be reported to BMS Drug Safety and Oncoceutics immediately by facsimile, email, or other appropriate method (to be done by BrUOG), using the required reporting forms (Forms to be completed by site and sent to BrUOG).

The Investigator will follow the subject until completion of the pregnancy, and must notify BMS and Oncoceutics (by informing BrUOG) of the outcome as specified below. The Investigator will provide this information as a follow-up to the initial report. If the outcome of the pregnancy meets the criteria for immediate classification as a SAE (i.e., spontaneous abortion [any congenital anomaly detected in an aborted fetus is to be documented], stillbirth, neonatal death, or congenital anomaly), the Investigator should follow the procedures for reporting SAEs (i.e., report the event to BrUOG who will then report to BMS and Oncoceutics by facsimile or email within 1 working day of being made aware of the event via the sites formal submission of the SAE pregnancy forms).

The patient should be referred to an obstetrician/gynecologist experienced in reproductive toxicity for further evaluation and counseling.

All neonatal deaths that occur within 100 days of birth should be reported, without regard to causality, as SAEs. In addition, any infant death after 100 days that the Investigator suspects to be related to the in-utero exposure to the study drug should also be reported. In the case of a live "normal" birth, BMS and Oncoceutics should be advised as soon as the information is available (BrUOG will advise BMS once information is submitted to BrUOG).

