Based on its mechanism of action and data from animal studies, Opdivo can cause fetal harm when administered to a pregnant woman. In animal reproduction studies, administration of nivolumab to cynomolgus monkeys from the onset of organogenesis through delivery resulted in increased abortion and premature infant death. Advise pregnant women of the potential risk to a fetus. Advise females of reproductive potential to use effective contraception during treatment with an Opdivo-containing regimen and for at least 5 months after the last dose of Opdivo [see Use in Specific Populations in the drug packaging insert]

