5.3 Contraception

During the study, fertile female patients must take precautions to prevent pregnancy since the effects of the study medication on the fetus are unknown. Male patients with partners of childbearing potential must take precautions to prevent pregnancy of the partner since the effects of this drug on sperm are unknown. These restrictions should remain in force for 5 months from the last dose of investigational agent (Nivolumab or ONC201) for WOCBP and for 7 months from the last dose of investigational agent (Nivolumab or ONC201). Drug interaction studies with oral contraceptives have not been performed, so barrier methods of contraception or abstinence should be considered. The definition of effective contraception should be in agreement with local regulation and based on the judgment of the principal investigator or a designated associate. A suggested definition of adequate contraception is the use of double barrier contraception (e.g., condom plus spermicide in combination with a female condom, diaphragm, cervical cap or intrauterine device).

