The initial report must be as complete as possible, including an assessment of the causal relationship between the event and the investigational product(s), if available. Information not available at the time of the initial report (e.g., an end date for the adverse event or laboratory values received after the report) must be documented on a follow-up report.

A final report to document discharge from hospital (or end of important medical event) is required.

All deaths during treatment or within 100 days (+ 1 week) following completion of active protocol treatment (Nivolumab or ONC201, whichever is last) must be formally reported to BrUOG within 5 business days of being made aware of the event or as soon as the investigator is made aware of the event. If the death is thought to be related to the study treatment (Nivolumab and/or ONC201), deaths must be reported to BrUOG within 24 hours of the investigator being made aware of the event.

All adverse events and special reporting situations, whether serious or non-serious, related or unrelated, will be reported from the time a signed and dated ICF is obtained until 100 days (+1 week) after the last treatment (Nivolumab or ONC201, whichever is last), or until the subject withdraws consent from study participation (declines participation) or at the time patient becomes a screen failure, whichever occurs first. There will be a safety visit at 30 days (+1 week) and 100 days (+1 week) time points.

Every adverse event, serious or non-serious, must be assessed by the investigator with regard to whether it is considered immune-mediated.

Serious adverse events occurring more than 100 days (+1 week) after study discontinuation need only be reported if a relationship to the study treatment (Nivolumab and/or ONC201) is suspected.

12.5.3 Types of Report: Guidelines for sites to report:

Telephone report: For SAE's contact the BrUOG office within 24 hours of learning of a SAE. For SAE notification: (initial and follow-up) contact BrUOG Central Office [contact] (or via email), with 24 hour notice prior to submitting a SAE report.

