Written report: Send the signed MedWatch 3500A form (and BMS pregnancy reporting form for pregnancies if applicable) within 5 business days of being made aware of the event to the BrUOG Central Office by email. For Follow-up reports, please submit the signed MedWatch 3500A when new information has become available and the event can be closed out.*Of note Oncoceutics will not receive BMS pregnancy form, just the Medwatch3500A*

Brown University Oncology Research Group

[contact], [contact]

Emails: [contact]

All deaths during treatment or within 100 days (+ 1 week) following completion of active protocol treatment (Nivolumab or ONC201, whichever is last) must be reported within 5 business days (from when site was made aware of the event) or as soon as the investigator is made aware of the event. If the death is thought to be related to the study treatment (Nivolumab and/or ONC201), **deaths must be reported to BrUOG within 24 hours of the investigator being made aware of the event. SAEs post 100 days since last dose of drug (+1 week) that are thought to be possibly related to study treatment** (Nivolumab or ONC201, whichever is last) **must be reported to BrUOG within the 5-business day time frame noted above.**

MedWatch 3500A Reporting Guidelines:

In addition to completing appropriate patient demographic and suspect medication information, the report should include the following information within the Event Description (section 5) of the MedWatch 3500A form:

- Treatment regimen (dosing frequency, combination therapy): if related to treatment regimen add to section C suspect product, if not related to any, add to concomitant section noting Lot #
- Protocol description (and number, if assigned)
- **Description of event, severity, treatment, and outcome, if known**

- **Action taken with Nivolumab and ONC201 as a result of the SAE and expectedness (based on IB and consent)**
- Supportive laboratory results and diagnostics
- Investigator's assessment of the relationship of the adverse event to **each investigational product** (Nivolumab) and suspect medication/treatment (ONC201) and if event(s) is/are immune mediated
- Documentation if the event(s) are considered immune mediated
- Site to be clear to outline which events are being reports as serious
- Must be typed
- ****It is required that sites put the following numbers on the MedWatch form for tracking:**
 - **BrUOG 379**
 - **INSERT BMS tracking # CA209-79E**

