d. Total serum bilirubin \leq 1.5 X upper limit of normal (ULN) (y/n)

e. AST (SGOT)/ALT (SGPT) \leq 2 X ULN; \leq 5 X ULN if liver dysfunction is felt to be secondary to tumor burden within 14 days prior to treatment (this is Day -7) (y/n)

f. Serum creatinine \leq 1.5 X ULN (OR creatinine clearance \geq 60 mL/min/1.73 m²) within 14 days prior to treatment (this is Day -7) (y/n)

g. Serum or urine pregnancy test (for females of childbearing potential) negative \leq 7 days of treatment (this is Day -7) _____ (y/n)

_____ (y/n) Ability to understand and the willingness to sign a written informed consent document and comply with the study scheduled visits, treatment plans, laboratory tests and other procedures.

_____ (y/n) Female patients of child-bearing potential must be practicing an effective form of contraception from the time of informed consent and for the duration of the study treatment through 5 months after the last dose of drug (ONC201 or Nivolumab, whichever is administered last). The decision of effective contraception will be based on the judgment of the principal investigator or a designated associate.

_____ (y/n) Male patients who are with women of child-bearing potential must be surgically sterile (provide date of surgery) or must agree to use effective contraception from the time of informed consent and for the duration of the study treatment through 7 months after the last dose of drug (ONC201 or Nivolumab, whichever is administered last). The decision of effective contraception will be based on the judgment of the principal investigator or a designated associate.

_____ (y/n) Patients must agree to the required tumor biopsies to enroll in the trial. Pre-treatment biopsies can occur any time post consent and prior to run-in ONC201 dose, a second biopsy will be required at the end of cycle 2 to assess response biomarkers, a final biopsy is included at the time of progression to assess for resistance mechanisms. Only 2 biopsies will be required for patients who initially progress at time of 2nd biopsy.

Exclusion

_____ (y/n) Patients with symptomatic brain metastases are excluded. Patients with asymptomatic and treated CNS metastases may participate in this trial. The patient must have completed any prior treatment for CNS metastases $>$ 28 days prior to registration, including radiotherapy or surgery. Steroids for the treatment of brain metastasis are not permitted.

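### The 100-day pregnancy reporting limit in Section 12.5.1 conflicts with Sections 12.5.2 and 12.6, falls short of the protocol's 5- and 7-month contraception periods, and comes with no written route for partner pregnancies

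*Combined protocol and SAP*

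**What the plan says.** **Reporting window.** Section 12.5.1 opens with "Pregnancies occurring while the subject is on study drug or within 100 days (+1 week) after" the last treatment. That sentence names no sex. A later sentence in the same section repeats the limit for pregnancies and suspected pregnancies "of a female subject occurring while the subject is on treatment (Nivolumab and/or ONC201), or within 100 days" (+1 week).

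**General closing point.** Sections 12.5 and 12.5.2 end the collection of adverse events and special reporting situations at 100 days (+1 week) after the last treatment. Section 12.4.3 has pregnancy handled as an SAE. Under 12.5.2, later SAEs "need only be reported if a relationship to the study treatment (Nivolumab and/or ONC201) is suspected".

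**Text without a window.** Section 12.5.2 begins by asking sites to report every pregnancy, confirmed or suspected, and any suspected fetal exposure, within 24 hours of awareness. Section 12.6 has the coordinating office send both companies any pregnancy associated with use of their products. Neither sets a time limit or names a sex.

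**Contraception periods.** Section 2.2.3 advises women to use contraception "for at least 5 months after the last dose of Opdivo". Inclusion criterion 12 in Section 5.1 also gives 5 months. Section 5.3 reads "These restrictions should remain in force for 5 months from the last dose of investigational agent (Nivolumab or ONC201) for WOCBP and for 7 months", without saying to whom the 7 months apply. The Appendix A checklist applies it to men with partners of childbearing potential: "for the duration of the study treatment through 7 months after the last dose of drug". Section 5.1 has no corresponding male criterion.

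**Form deadline.** Section 12.5.1 wants the pregnancy form and the MedWatch form within 24 hours. Section 12.5.3 allows the MedWatch form "and BMS pregnancy reporting form for pregnancies if applicable) within 5 business days".

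**The concern.** Embryo-fetal toxicity is a named risk of nivolumab: Section 2.2.3 cites increased abortion and premature infant death in monkeys and ties the 5-month contraception advice to it. Section 5.3 says the effects of study medication on the fetus and on sperm are unknown, and asks men to prevent pregnancy in a partner. A protocol that asks for precautions over a stated period should collect the pregnancies that occur in it. The section titled for pregnancies stops earlier, and it describes follow-up only of the subject, not of a subject's partner.

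At stake is the completeness of a small but important body of safety data. Fetal exposures that nobody asks about at the time are difficult to reconstruct later.

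**Working it through.** No power or error-rate figure is involved. The check compares windows in days and then asks which text a site would follow.

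**Inputs**
- Reporting window: 100 days, or 107 if the extra week counts (Section 12.5.1).
- Women: 5 months after last dose (Sections 2.2.3, 5.1 and 5.3; Appendix A).
- Men: 7 months after last dose (Appendix A; Section 5.3 without the sex).
- Assumption: 30.4375 days per month, with 30 days as the low variant.

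**Formulas:** period = months × days per month; gap = period − reporting window; share = gap ÷ period.

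| Group | Days per month | Period (days) | Gap against 107 | Gap against 100 | Share of period |
|---|---|---|---|---|---|
| Women | 30.4375 | 152.2 | 45.2 | 52.2 | 29.7–34.3% |
| Women | 30 | 150 | 43 | 50 | 28.7–33.3% |
| Men | 30.4375 | 213.1 | 106.1 | 113.1 | 49.8–53.1% |
| Men | 30 | 210 | 103 | 110 | 49.0–52.4% |

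The men's rows read the first sentence of 12.5.1 as covering partners. If only female subjects are covered, 12.5.1 reaches none of the men's period.

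**Which text applies to a pregnancy beginning on day 120?**
1. Section 12.5.1: past 107 days, so not reportable.
2. Sections 12.5 and 12.5.2, general window: closed.
3. Section 12.5.2, late SAEs: reportable only if a relationship to treatment is suspected. That test suits a pregnancy poorly, because what matters is exposure, not whether the drug caused the pregnancy.
4. Section 12.5.2, opening sentence: reportable within 24 hours of awareness.
5. Section 12.6: to be forwarded, but the office can forward only what a site has submitted.

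Items 1 and 4 give opposite answers.

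**Would the pregnancy come to light?** Section 8 marks pregnancy tests only in the treatment cycles. The last safety visit is at 100 days (+1 week). Later contacts, about every 3 months (±1 month) for 6 months, are specified for survival and disease status. No scheduled procedure after the 100-day visit asks about pregnancy.

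**The case against.** The strongest reply is that the protocol already contains an unrestricted duty. The opening of 12.5.2 and the text of 12.6 ask for all or any pregnancies, and the 12.5.2 wording on suspected fetal exposure could reach a partner. Section 12.5.1 also requires neonatal deaths within 100 days of birth to be reported regardless of causality, and later infant deaths when in-utero exposure is suspected. An abortion or congenital anomaly after day 100 could be judged treatment-related and reported. The 100-day limit matches the general safety window.

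Much of this stands. From 12.5.1 alone a reader might infer that later pregnancies are excluded by design, that only female subjects are covered, that partner pregnancies are never collected, or that each such case is lost completely. The documents do not support those readings. The first sentence of 12.5.1 names no sex, 12.5.2 and 12.6 carry no window, and a route for related late SAEs exists. Nor does the protocol call the 5 and 7 months fetal-risk windows. They are contraception periods; Section 2.2.3 links the 5 months to fetal harm, while for men Section 5.3 says only that effects on sperm are unknown.

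The reply does not remove the conflict. The opening of 12.5.2 sets a deadline after awareness, whereas 12.5.1 is the section that defines a reporting period, and Section 12.4.3 sends the reader elsewhere for pregnancy.

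Two related points are narrower than they look. Section 5.3 already binds male patients, so the missing item in 5.1 is a drafting mismatch. Section 12.5.2 reserves the 5-business-day allowance for other SAEs, so the timing conflict concerns only the written forms in 12.5.3.

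**Conclusion.** The point holds as an internal inconsistency with a practical consequence. A site following 12.5.1 may not report a pregnancy that begins in the last 45–52 days of the women's contraception period (30–34%) or the last 106–113 days of the men's (50–53%). No partner pathway, partner consent or partner outcome follow-up is written out.

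The sizes assume average-length months, and each range reflects whether the extra week counts. They are shares of calendar time, not of pregnancies. The documents give no basis for an expected number of pregnancies; with 34 patients planned at the recommended phase II dose, few would be affected. Objectives, endpoints, power and type I error are unchanged. The sponsor should correct this because the exposure data are hard to recover once missed and the correction is cheap.

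**What to change.** 1. Reconcile Sections 12.5, 12.5.1 and 12.5.2 (and check 12.6) so that the pregnancy reporting window matches the protocol's own contraception periods: 5 months after last dose for female subjects and 7 months for partners of male subjects.
2. State that partner pregnancies are reportable, with partner consent for outcome data.
3. Add a pregnancy question to the existing follow-up contacts at about 3 and 6 months. Month 7 falls within the +1 month allowance of the 6-month contact; otherwise it needs one extra call.
4. Give one deadline for the pregnancy forms across 12.5.1, 12.5.2 and 12.5.3.
5. Reconcile Section 5.1 with 5.3 and Appendix A on male contraception, and name the group to which the 7 months in 5.3 apply.

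The cost is amendment wording, one question at planned contacts, a partner consent form and possibly one telephone call per male patient with a partner of childbearing potential. No visit is added.
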